6.2. Inclusion Criteria

Subjects who meet all of the following criteria may be given consideration for inclusion in this clinical investigation, provided no exclusion criterion (see Section 6.3) is met.

- 1. 18 years or older
- 2. Abdominal pain consistent with choledocholithiasis (possible procedure within 72 hours of onset of symptoms and imaging suggesting choledocholithiasis, contingent on persistent abdominal pain)
- 3. Abnormal LFTs

4. Non-complex biliary stone disease, defined as 5 or fewer stones in the common bile or common hepatic duct with largest stone no larger than 10 mm in size. If stones not seen on imaging (US, CT) the bile duct diameter should be ≤12 mm.*

* Given the poor sensitivity (approximately 20%) for biliary stones of CT and US, the diameter of the dilated CBD is used as a surrogate for largest stone diameter

- 5. Availability of prior non-invasive imaging to determine the diameter of the bile duct and number and size of bile duct stones if visible on imaging.
 - a. If probability of stones is high per investigator assessment based on ASGE criteria, any standard of practice imaging modality (eg. abdominal US) is acceptable. (see Figure 22.3-1, page 49).
 - b. If the probability of stones is either intermediate or low per investigator assessment based on ASGE criteria, MRCP or EUS imaging is required to confirm presence of stones. (see Figure 22.3-1, page 49).
- 6. Willing and able to comply with the study procedures and provide written informed consent to participate in the study.

6.3. Exclusion Criteria

Subjects who meet any one of the following criteria will be excluded from this clinical study.

- 1. Potentially vulnerable subjects, including but not limited to pregnant women and subjects in whom an endoscopic procedure is contraindicated.
- 2. Location of the stones in intrahepatic ducts, cystic duct or proximal to strictures
- 3. Bile duct stricture noted distal to stone on MRCP, which would make extraction without lithotripsy impossible.
- 4. Ongoing cholangitis at time of randomization, manifested by fever with tachycardia and hypotension or evidence of pus at the ampulla
- 5. Patients with prior biliary sphincterotomy
- 6. Patients with Primary Sclerosing Cholangitis (PSC)
- 7. Acute pancreatitis, defined as abdominal pain and serum concentration of pancreatic enzymes (lipase (required), amylase (optional) three or more times the upper limit of normal.
- 8. Surgically altered gastro-duodenal luminal anatomy other than prior Billroth I reconstruction, as these would be anticipated to lead to more complicated procedures.
- 9. Coagulopathy or ongoing need for anti-coagulation

7. Subject Accountability

7.1. Point of Enrollment

Patients who are considered for participation into the study but do not provide informed consent or do not meet eligibility criteria are considered screen failures. Screen failures will be tallied at each study site.

In the case it is determined that the patient failed to meet the inclusion/exclusion criteria after the patient has agreed to participate in the study and has signed the informed consent, the study personnel will complete the Screening form as well as the End of Study form and indicate the specific inclusion/exclusion criterion that was not met.

7.2. Withdrawal

Subjects will participate in the study voluntarily and may withdraw at any time without prejudice to further treatment. If a subject withdraws from the clinical investigation, the primary reason shall be reported.

All applicable case report forms up to the point of subject withdrawal, including an End of Study form must be completed.

Subjects who are "lost-to-follow-up" should have three documented attempts to contact them prior to completion of the End of Study form. If withdrawal is due to investigator's discretion, the investigator will describe what follow-up activities the investigator is obligated to perform.

Unless the withdrawal is due to a Serious Adverse Event, additional subject data will not be collected after the point at which the subject has been withdrawn or withdraws consent from the study. Data collected up to the point of withdrawal may be used by the investigators as permitted in the ICF.

8. Study Methods

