4.2. Secondary Endpoint

The following will be recorded as secondary outcomes during baseline and follow-up procedures:

- 1. Evaluation of all serious adverse events (SAEs) including all deaths (related and unrelated), severity, onset, time to resolution related to the DSC devices and/or procedure and/or the ERC procedure through 30 days post procedure.
- 2. Radiation exposure to the patient (total fluoroscopy time, total radiation dose, Dose Area Product (DAP), effective dose), from duodenoscope in to completion of stone clearance, not including the validation DSC procedure in ERC arm and ERC procedure in DSC arm.

3. Duration of procedure defined as time from duodenoscope in to completion of stone clearance, not including the validation DSC procedure in ERC arm and ERC procedure in DSC arm.

5. Study Design

This is a prospective, multi-center, randomized controlled study comparing endoscopic clearance of non-complex biliary stones using fluoroscopy/radiation free direct solitary cholangioscopy (DSC) versus standard of care endoscopic retrograde cholangiography (ERC) at up to 15 global sites.

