- If clear fluid is aspirated, this may indicate that the pancreatic duct has been accessed. Re-attempt to access the bile duct. If no fluid is aspirated, or if there is remaining uncertainty over which duct was accessed, physicians if they wish, may use a brief tap on the fluoroscopy pedal to assess whether the guidewire appears to be in the bile duct. Alternatively, they may proceed to an early double wire and/or transpancreatic septotomy cannulation technique. They MUST proceed to double wire and/or transpancreatic septotomy cannulation techniques if fluoroscopy-free cannulation failure persists for 15 minutes. If brief fluoroscopy is used to confirm biliary cannulation, then the case is considered a primary endpoint failure, but the DSC technique for stone evaluation and clearance may be continued. Secondary endpoints will be assessed in these patients, including patient radiation exposure.
- If initial fluoroscopy-free cannulation failure persists for 15 minutes, a double wire and/or transpancreatic septotomy cannulation technique should be attempted.
- If cannulation failure persists despite these advanced cannulation techniques for an additional 15 minutes, this will be considered a **cannulation failure**. The patient will **crossover to the ERC arm** where these cannulation techniques will be continued with full fluoroscopy support. If cannulation in the ERC arm fails despite use of fluoroscopy and basic/advanced cannulation techniques for an additional 15 min then participating institutions may then proceed with their standard of care interventions at this point. Use of needle-knife other than for visibly impacted stones will be considered a cannulation failure for these crossover patients.
- Patients will be followed through 30 days post index procedure as indicated in the follow-up schedule.
- 3. After fluoroscopy-free cannulation succeeds, biliary sphincterotomy will be performed. Additional papillary large balloon dilation can be performed if the sphincterotomy is felt to be inadequate
- 4. The sphincterotome will be exchanged for the SpyGlass cholangioscope over the guidewire.
- 5. The cholangioscope will be advanced into the bile duct up to the bifurcation (hilum) and distance from ampulla to the bifurcation (hilum) will be noted. (Adhesive tapes placed on SpyGlass shaft where it exits the duodenoscope working channel when cholangioscope is at the bifurcation, and again when it just exits ampulla will allow measurement of this distance).

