8.8. Study Completion

Subjects will be followed for 30 days post-index procedure. At study completion, an End of Study form will be completed, indicating whether the subject completed the study. If the last follow-up visit was not completed, the investigator will note the reason on the study completion form (e.g. subject withdrawn by investigator, subject withdrew consent, lost to follow-up, SAE, death, etc.).

9. Statistical Considerations

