7.3 Rules and Definitions

- Binary event rates (proportions) will be reported on a per-patient basis.
- The last follow-up date will be the latest of the following dates for each patient: date of an adverse event, procedure date, follow-up visit date, and device event date.
- Serious Adverse Event will be defined as an adverse event that:
 - Led to death
 - Led to a serious deterioration in the health of the subject that either resulted in:
 - a life-threatening illness or injury, or
 - a permanent impairment of a body structure or a body function, or
 - in-patient hospitalization or prolonged hospitalization (of an existing hospitalization), or
 - medical or surgical intervention to prevent life-threatening illness or injury or permanent impairment to a body structure or a body function
 - Led to fetal distress, fetal death, or a congenital abnormality or birth defect.
- When calculating rates of adverse events, missing and partial dates will be handled as follows:

Partial Date Description	Action Taken
Entire onset date is missing	The procedure date will be used for the
	onset date.

Form/Template 90702621 Rev/Ver AE < Non-Complex Biliary Stones RCT, document 92232577, Rev/Ver AA > Page 12 of 13

Partial Date Description	Action Taken
The month and the day of the month are	January 1 will be used for the month and
missing but the year is available	day of the onset date. However, if the
	imputed date falls before the procedure
	date, then the procedure date will be used
	for the onset date.
Day is missing, but the month and year are	The 1 st will be used as the day of the onset
available	date. However, if the imputed date falls
	before the procedure date, then the
	procedure date will be used for the onset
	date.

Form/Template 90702621 Rev/Ver AE < Non-Complex Biliary Stones RCT, document 92232577, Rev/Ver AA > Page 13 of 13

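### Protocol 7.2 stops data collection for patients the investigator withdraws, even when they still consent, unless an SAE caused the withdrawal; 30-day safety data are lost selectively among withdrawn patients

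*Protocol*

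**What the plan says.** Protocol 7.2 sets the rule: "Unless the withdrawal is due to a Serious Adverse Event, additional subject data will not be collected after the point" of withdrawal. Two groups fall under it, since the sentence speaks of when "the subject has been withdrawn or withdraws consent from the study". Withdrawal due to an SAE is the only stated exception.

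The same section adds: "If withdrawal is due to investigator's discretion, the investigator will describe what follow-up activities the investigator is obligated to perform".

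Protocol 8.8 treats investigator withdrawal and consent withdrawal as different reasons for ending the study. Its examples are "subject withdrawn by investigator, subject withdrew consent, lost to follow-up, SAE, death".

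The first secondary endpoint (Protocol 4.2; SAP 5.1) covers SAEs, including all deaths, "related to the DSC devices and/or procedure and/or the ERC procedure through 30 days post procedure". Protocol 8.7 collects these by telephone at 24 hours, 7 days and 30 days, together with every case of cholangitis, pancreatitis, perforation or bleeding, serious or not, and device events.

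Elsewhere the protocol holds on to 30-day follow-up. For cannulation and extraction failures, 8.6 says: "Patients will be followed through 30 days post index procedure as indicated in the follow-up schedule". Section 19.4 does the same for patients at a terminated site.

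SAP 7.3 says: "Binary event rates (proportions) will be reported on a per-patient basis". It defines a last follow-up date for each patient but gives no rule for patients who leave before day 30.

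**The concern.** Ending collection is necessary when a patient refuses further data collection. It is not necessary when the investigator withdraws a patient who would still take the calls, yet 7.2 handles both alike.

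The exception also makes the loss selective. A patient withdrawn because of an SAE already counts as having an event in a per-patient rate, and that patient's collection may continue. A patient withdrawn for any other reason is the one whose first SAE could still occur, and that patient's data stop. A patient withdrawn after a non-serious cholangitis, pancreatitis, perforation or bleed is also dropped, although all such events are meant to be collected and some could worsen.

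At stake is completeness of the 30-day safety comparison in an unblinded trial (Protocol 8.5). The direction of error is known, since unrecorded events understate harm, and data not collected at the time may not be recoverable later.

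**Working it through.** **1. Does the stop reach consenting patients?** The rule joins two groups with *or*: those who have been withdrawn and those who withdraw consent. Section 8.8 confirms that these are separate categories. So yes.

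**2. Does other text lift the stop?**

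- *7.2, investigator's discretion.* The investigator must describe obligated follow-up activities. No 30-day contact, SAE enquiry or data entry is required, and the sentence is not written as an exception.
- *17.1.* Any adverse event the protocol requires, arising after enrolment and during or after the procedure, must be recorded. Withdrawn patients are not mentioned.
- *17.4, reporting table.* SAE reporting runs through the end of study. Since 7.2 has an End of Study form completed at withdrawal, this does not clearly extend past it.
- *8.6 and 19.4.* These keep 30-day follow-up for procedural failures and terminated sites. They do not address withdrawn patients.

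No passage overrides the stop. The passages stand beside it unreconciled.

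**3. Primary endpoint and sample size.** The plan states 250 patients (125 per arm) for 90% clearance in both arms, a 10% margin, one-sided alpha 0.05 and 80% power. An exact unconditional non-inferiority test with Farrington–Manning score ordering gives 81.7% power at 125 per arm and 80.5% at 124 per arm, so the figure reproduces. Clearance is determined at the index procedure, so a stop on later data does not touch it.

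**4. Size of the safety loss.** The documents give neither a withdrawal rate nor a 30-day SAE rate for this trial. These inputs are assumptions:

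- w = proportion withdrawn for a reason other than an SAE: 2% to 10%
- r = 30-day SAE risk per patient: 5% to 10%
- f = share of that risk falling after withdrawal: 25% to 50%
- withdrawal unrelated to later risk

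Expected patients with a missed SAE per arm = 125 × w × r × f. Observed rate over the full arm = r − w × r × f.

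| w | r | f | Missed per arm | Observed rate |
|---|---|---|---|---|
| 2% | 5% | 25% | 125 × 0.02 × 0.05 × 0.25 = 0.03 | 4.98% |
| 5% | 5% | 50% | 125 × 0.05 × 0.05 × 0.50 = 0.16 | 4.88% |
| 5% | 10% | 50% | 125 × 0.05 × 0.10 × 0.50 = 0.31 | 9.75% |
| 10% | 10% | 50% | 125 × 0.10 × 0.10 × 0.50 = 0.63 | 9.50% |

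The largest understatement is 10.0% − 9.5% = 0.5 percentage points. The loss is proportional to the later risk of those withdrawn, so it grows if withdrawal tracks a developing complication.

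**The case against.** The strongest reply is that few patients can be affected. Treatment is one procedure followed by three telephone calls, so there is no continuing study treatment to stop. Patients found ineligible before randomization are screen failures, and consent withdrawals rightly end collection. What remains is non-SAE withdrawal by the investigator within 30 days. The SAP plans no hypothesis test on safety, and 17.1 and 17.4 show that events were meant to be reported. All of this stands as to size. It does not change what 7.2 instructs a site to do.

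Four stronger readings are tempting, and the documents do not support them:

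- *That 7.2 contradicts 8.6.* Cannulation failure, extraction failure and crossover are protocol outcomes, not withdrawals, and 8.6 keeps those patients in follow-up. The passages meet only if such a patient is later withdrawn.
- *That failed procedures, especially in the DSC arm, will be the ones withdrawn.* Nothing says so, and sites are told to follow exactly these patients. A differential loss between arms is possible but has no figure behind it.
- *That the SAP counts withdrawn patients as event-free.* Per-patient reporting means counting patients rather than events. The SAP does not define the denominator for patients who leave early.
- *That the pilot figures give the size.* Protocol section 1 reports 4 + 3 + 1 = 8 complications in 81 patients (9.9%). These are post-procedure complications, not SAEs, and applying the whole rate to withdrawn patients assumes that all the risk falls after withdrawal.

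**Conclusion.** The point holds, within limits. Read as written, 7.2 ends data collection for consenting patients withdrawn by the investigator and makes an SAE-related reason the only way to remain under observation. The dependence on outcome applies among withdrawn patients only, not to the 30-day follow-up of the whole cohort. The expected loss is about 0.03 to 0.63 patients with an SAE per arm, at most 0.5 percentage points. That rests on assumed withdrawal and SAE rates and on withdrawal being unrelated to later risk; if it is related, the loss is larger. The primary analysis is not at risk. This is a cheap improvement worth making rather than a threat to the trial's conclusion.

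**What to change.** **Protocol 7.2.** Reword the stop so that collection ends only when the patient withdraws consent to further data collection. Patients withdrawn for any other reason should continue the 24-hour, 7-day and 30-day safety calls already scheduled, with the content of 8.7. Reconcile this with the sentence on investigator-discretion withdrawal and with the reporting duties in 17.1 and 17.4.

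**SAP 7.3.** Report by arm the number of patients not followed to 30 days, next to the 30-day event rates, and state how those patients enter the denominator.

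A sensitivity analysis limited to patients followed to 30 days or with an event should be left out, or labelled an upper bound, because inclusion depends on the outcome. It keeps early leavers with an event and drops those without. Under the assumptions above its rate is (r − w × r × f) / (1 − w × (1 − r × (1 − f))). With w = 10%, r = 10% and f = 50% this is 0.095 / 0.905 = 10.5%, against a true 10.0%.

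**Cost.** One reworded protocol passage, a check that the consent form covers continued calls, a few extra calls, and one added line in the safety table.

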8.1. Data Collection

Data collection will occur according to the Data Collection Schedule shown in Table 8.1-1.

	Screening	Baseline	Index Procedure				
Procedure/Assessment				24 hours Telephone Follow-up	7 Days (± 2 Days) Telephone Follow-up	30 Days (± 10 Days) Telephone Follow-up	Unscheduled Reintervention
Informed consent, Inclusion/Exclusion Criteria	х						
Demographics		Х					

Table 8.1-1: Data Collection Schedule

Non-Complex Biliary Stones DSC vs ERC RCT Template 90702637 Rev/Ver AH Page 20 of 51

Procedure/Assessment	Screening	Baseline	Index Procedure	24 hours Telephone Follow-up	7 Days (± 2 Days) Telephone Follow-up	30 Days (± 10 Days) Telephone Follow-up	Unscheduled Reintervention
Non-Invasive Imaging (Ultrasound, CT or MRCP)		Х					
Medical history		Х					
Lab Results		Х					
Probability of bile duct stone based on ASGE criteria: high, intermediate or low		х					
Need for MRCP or EUS based on intermediate or low ASGE criteria		Х					
Procedural details			Х				
Post-procedure Follow up				X	Х	Х	
Biliary Re-interventions				X	Х	Х	X
Serious Adverse Events assessment			X	X	Х	X	

8.2. Study Candidate Screening

Patients who present with abdominal symptoms of choledocholithiasis, or who have undergone imaging demonstrating choledocholithiasis as listed in Inclusion Criteria will be screened for trial enrollment. A Screen Failure/Enrollment Log will be maintained by the center to document select information about candidates who signed consent.

8.3. Informed Consent

Data collection or study procedure will not occur prior to the patient signing the ICF. Patients will be considered enrolled in the study once they sign the informed consent and affirm that they agree to participate in the study and adhere to the study schedule. Once a patient is considered enrolled in the study, baseline information may be obtained.

8.4. Baseline

The following baseline data will be collected for all subjects:

- Demographics
- Results of Non-Invasive Imaging (including Ultrasound, CT or MRCP)
- Medical History
- Lab Results (LFTs, Lipase, Hct, Platelet Count)
- Probability of bile duct stone based on ASGE criteria: high, intermediate or low
- Need for MRCP or EUS based on intermediate or low ASGE criteria

8.5. Randomization

Randomization is to occur only after verification of all inclusion/exclusion criteria. Once the patient has signed the IRB/EC-approved study ICF and has met all general inclusion and none of the exclusion criteria, the patient will be eligible for randomization.

Randomization will be stratified by clinical site. Within each site, eligible subjects will be randomized in a 1:1 ratio to receive each treatment method. This study is not blinded.

For back-up randomization, sites will be instructed to randomize patients via back-up envelopes only in cases of unsuccessful access to the online database system. Envelopes are sequentially numbered sealed opaque envelopes containing randomized treatments.

8.6. Procedure

The following procedural data will be collected for all subjects:

- Achievement of cannulation portion of procedure
- Biliary Sphincterotomy performed
- Additional sphincteroplasty performed

- Number and approximate size of stones extracted
- Time Stamps:
 - o Duodenoscope in
 - Time cannulation commenced
 - Time biliary cannulation achieved (defined as free advancement of guidewire)
 - SpyGlassTM DS in (For DSC Procedure)
 - SpyGlassTM DS out (For DSC procedure)
 - Time stone clearance achieved
 - Duodenoscope out
- Total radiation exposure to patient (fluoroscopy time, total radiation dose, Dose Area Product (DAP), effective dose)
- Volume of injected saline during DSC procedure
- Total number of endoscopic devices used during the procedure.
- Procedure outcome: all stones successfully extracted during the procedure?
- Serious Adverse Events and Device Events and all cases of Cholangitis, Pancreatitis, Perforation and Bleeding.

The following steps are procedural guidelines:

In both arms:

- 1. Prior non-invasive imaging will be reviewed to determine the number and size of bile duct stones (if possible) and the diameter of the bile duct.
- 2. Once bile duct stones are deemed to be a high probability based on clinical presentation imaging and ASGE criteria, patients will be randomized to either the DSC arm or the ERC arm.
- 3. Patient will receive prophylactic antibiotics and rectal indomethacin.
- 4. The duodenoscope will be advanced to the duodenum and the major papilla will be identified.
- 5. Needle knife pre-cut sphincterotomy may be utilized for stones visibly impacted at the ampulla.
- 6. A sphincterotome with guidewire will be used to cannulate the bile duct following needle knife sphincterotomy AND for all other patients without visibly impacted stones.

In Group A (ERC arm):

1. Needle knife pre-cut sphincterotomy may be utilized for stones visibly impacted at the ampulla.

- 2. For all other patients, standard cannulation techniques with a sphincterotome to gain biliary access; contrast medium injected.
- 3. If initial cannulation has not been achieved within 15 minutes, a double wire technique and/or transpancreatic septotomy cannulation technique should be attempted.
- 4. If cannulation failure persists despite these advanced cannulation techniques for an additional 15 minutes, this will be considered a **cannulation failure**. Participating institutions may proceed with their standard of care interventions at this point.
- 5. Use of needle-knife other than for visibly impacted stones will be considered a **cannulation failure.** Patients will be followed through 30 days post index procedure as indicated in the follow-up schedule.
- After cannulation succeeds, number and estimated size of biliary stones will be confirmed following contrast injection. Biliary sphincterotomy will be performed. Additional papillary large balloon dilation can be performed if the sphincterotomy is felt to be inadequate.
- 7. Stone removal using standard techniques. If unexpectedly large stones are encountered, papillary large balloon dilation or mechanical lithotripsy may be applied.
- 8. If stone clearance fails due to size/shape of the stone(s), **stone extraction failure** will have occurred. However, participating institutions may proceed with their standard of care interventions at this point, including cholangioscopy and EHL/LL or stent placement with repeat ERC on another day. Patients will be followed through 30 days post index procedure as indicated in the follow-up schedule.

Post ERC validation by DSC:

- 9. In patients in whom stone extraction is deemed to be complete, the SpyGlass[™] cholangioscope will then be advanced to confirm complete clearance of the bile duct.
- 10. If residual stone(s) are noted, then additional balloon sweeps, and/or stone retrieval using a SpyGlassTM Retrieval Basket, of the bile duct will be performed with fluoroscopy assistance and supplemented by papillary large balloon dilation, mechanical lithotripsy and EHL/LL as needed.
- 11. The number of "missed stones" equal to or greater than 5 mm in size per endoscopist's estimate will be documented.

In Group B (DSC arm):

- 1. Needle knife pre-cut sphincterotomy may be utilized for stones visibly impacted at the ampulla.
- 2. Fluoroscopy-free cannulation technique to gain biliary access for all other patients.
 - Do not prime the sphincterotome with contrast.
 - Following deep cannulation, confirm free advancement of the guidewire into a ductal system.

- Aspiration of bile via the sphincterotome using a syringe to confirm bile duct cannulation.
- If clear fluid is aspirated, this may indicate that the pancreatic duct has been accessed. Re-attempt to access the bile duct. If no fluid is aspirated, or if there is remaining uncertainty over which duct was accessed, physicians if they wish, may use a brief tap on the fluoroscopy pedal to assess whether the guidewire appears to be in the bile duct. Alternatively, they may proceed to an early double wire and/or transpancreatic septotomy cannulation technique. They MUST proceed to double wire and/or transpancreatic septotomy cannulation techniques if fluoroscopy-free cannulation failure persists for 15 minutes. If brief fluoroscopy is used to confirm biliary cannulation, then the case is considered a primary endpoint failure, but the DSC technique for stone evaluation and clearance may be continued. Secondary endpoints will be assessed in these patients, including patient radiation exposure.
- If initial fluoroscopy-free cannulation failure persists for 15 minutes, a double wire and/or transpancreatic septotomy cannulation technique should be attempted.
- If cannulation failure persists despite these advanced cannulation techniques for an additional 15 minutes, this will be considered a **cannulation failure**. The patient will **crossover to the ERC arm** where these cannulation techniques will be continued with full fluoroscopy support. If cannulation in the ERC arm fails despite use of fluoroscopy and basic/advanced cannulation techniques for an additional 15 min then participating institutions may then proceed with their standard of care interventions at this point. Use of needle-knife other than for visibly impacted stones will be considered a cannulation failure for these crossover patients.
- Patients will be followed through 30 days post index procedure as indicated in the follow-up schedule.
- 3. After fluoroscopy-free cannulation succeeds, biliary sphincterotomy will be performed. Additional papillary large balloon dilation can be performed if the sphincterotomy is felt to be inadequate
- 4. The sphincterotome will be exchanged for the SpyGlass cholangioscope over the guidewire.
- 5. The cholangioscope will be advanced into the bile duct up to the bifurcation (hilum) and distance from ampulla to the bifurcation (hilum) will be noted. (Adhesive tapes placed on SpyGlass shaft where it exits the duodenoscope working channel when cholangioscope is at the bifurcation, and again when it just exits ampulla will allow measurement of this distance).
- 6. Injection of saline/water to be minimized to avoid driving stones more proximally (inject gently with a syringe rather than using the pump). Suction applied through the Spyglass cholangioscope and gentle 'head-up' tilt of the fluoroscopy table may be utilized.
- 7. Number and estimated size of biliary stones will be confirmed during cholangioscopy.

8. Visualized stones may then be extracted using a Balloon catheter and/or SpyGlass[™] Retrieval Basket.

Retrieval using Balloon Catheter:

- 9. The cholangioscope will be exchanged for a stone extraction balloon catheter. This exchange should be performed over a **long 0.035**" **guidewire**; if a short guidewire or a 0.025" guidewire was used earlier in the procedure, it should ideally be changed prior to next steps. The balloon catheter should be of appropriate size to fill the bile duct lumen (based on known diameter from prior non-invasive imaging). The balloon catheter will have distance markings.
- 10. A stone extraction balloon catheter marked with the distance from ampulla to hilum will then be advanced over the guidewire long 0.035" guidewire.
- 11. For patients with multiple stones, the balloon will be sequentially advanced more proximally up the bile duct for balloon sweeps, and eventually advanced to the hilum guided by previously measured distance from ampulla to hilum. Where only a single stone is noted, a single sweep commencing at the hilum may be performed. Balloon sweeps will be performed and the number of extracted stones will be counted to confirm complete extraction.
- 12. Saline irrigation will be performed via the balloon catheter, with the catheter positioned at proximal to the bifurcation prior to the last 2 balloon sweeps, to ensure clearance of any residual sludge/stone fragments/debris. If possible a gentle head up tilt of the table may be performed prior to irrigation to encourage downward movement of stones.
- 13. The cholangioscope will then be re-inserted and advanced to the hilum to confirm complete clearance of the bile duct.
- 14. If residual stone/stones are noted, additional balloon sweeps will be performed followed by repeat cholangioscopy to confirm clearance. This cycle may be repeated as necessary until all stones are believed to have been successfully extracted.

Retrieval using SpyGlassTM Retrieval Basket:

- 15. Stones visualized at cholangioscopy may also be captured and retrieved sequentially using the SpyGlass[™] Retrieval Basket, commencing distally and progressing proximally to the hilum as with balloon extraction. Extracted stones will be counted. If stone capture is difficult using the basket, the endoscopist may switch to balloon extraction at any point. Where retrieval is successful using purely SpyGlass[™] Retrieval Basket alone (without need for balloon catheter), or if retrieval using SpyGlass[™] Retrieval Basket is utilized for the final visualized stone, saline irrigation (Step 12) and cholangioscope reinsertion (Steps 13/14) will not be necessary.
- 16. EHL or LL may be performed for unexpectedly large/complex stones.
 - If stone clearance fails due to size/shape of the stone(s), electro-hydraulic lithotripsy (EHL) or laser lithotripsy (LL) can be performed.
 - If stone clearance still fails **stone extraction failure** will have occurred. However, participating institutions may proceed with their standard of care interventions at this point, including ERC with mechanical lithotripsy or stent

placement followed by repeat ERC on another day. Patients will be followed through 30 days post index procedure as indicated in the follow-up schedule.

Post DSC validation by ERC:

- 17. An occlusion cholangiogram will be performed using the stone extraction balloon catheter and presence or absence of filling defects will be documented.
- 18. If filling defects are noted, then balloon sweeps of the bile duct will be performed to determine if the filling defects are "missed" bile duct stones or simply air bubbles.

The number of "missed stones" > 5 mm per endoscopist's estimate will be documented.

8.7. 24-Hour, 7-Day, and 30-Day Follow-up

The following data will be collected for all subjects (including Roll-in cases) during these follow up periods:

- Phone call to patient
- Serious Adverse Events, all events of Cholangitis, Pancreatitis, Perforation, and Bleeding, and Device Events, including discharge summaries for any device-related hospitalizations.

